The tPBM treatment can be completed in the comfort of participants' homes, while monitoring their safety and response during scheduled medicine visits. The advantage of the tPBM treatment approach compared to pharmacotherapy is that adherence can be easily monitored. Our study will answer whether tPBM has an effect on ASD symptoms in ADHD and whether it is acceptable among our patients, for whom frequent visits otherwise would be prohibitive or render it inaccessible. As such, we propose the inclusion of a telemedicine visits in this study protocol.

II. SPECIFIC AIMS

The purpose of this 10-week open-label clinical study is to assess the tolerability, safety, and efficacy of Transcranial LED Therapy in youth patients with ADHD diagnosis who also present with at least moderate level of ATs.

Primary Objective:

- To assess the *efficacy* of tPBM for the treatment of ATs in youth with ADHD.
- To assess the *safety and tolerability* of tPBM for treatment of ATs in youth with ADHD

Secondary Objective:

- To evaluate the efficacy of tPBM in treatment of ADHD with ATs

Rationale for use of this device in patients with ASD:

Different devices have been used in study of near-infrared radiation (NIR) treatment effects in humans. We decided to use a new device, manufactured by Niraxx for its ease of application,

Photobiomodulation for ASD in ADHD

with safeguards to pose no risk of exposure to LED light. The device is designed as a simple headband, a common garment during most sports or leisure activities

III. SUBJECT SELECTION

Inclusion Criteria

- Male or female participants between 9 and 17 years of age (inclusive)
- Participant fulfills DSM-5 diagnostic criteria for ADHD as established by the clinical diagnostic interview.
- Participants with at least moderate severity of ASD symptoms as demonstrated by SRS raw score ≥ 75 or CGI-AT severity score ≥ 4
- Participants must understand the nature of the study. Participants must sign an IRB-approved informed consent form before initiation of any study procedures.
- Participants are willing and able to cooperate with all tests, examinations and demonstrate ability to appropriately administer the study treatment required by the protocol.
- Participants must have access to a computer with camera and broadband internet connection
- Participants have access to Apple IOS in their household.

Exclusion Criteria

Subjects will be excluded from the study for **any** of the following reasons:

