Any information and data collected during any subject's participation in this investigation will be considered confidential. The Investigator will need to ensure that all subjects' anonymity will be maintained on all documentation by completely redacting (eliminating or "blacking out") each subject's name and/or other identifying information. The identifying information will be replaced with the subject's study number. For the purpose of internal monitoring, Niraxx Inc. will use participants' email addresses to access treatment adherence and compliance data, which will be sent directly to the study team on a weekly basis via secure email and stored on a secure server at MGH. To protect subject confidentiality, Niraxx Inc. follows the General Data Protection Regulation (GDPR)— a European Union data protection and privacy regulation (42). Further, Niraxx Inc. will only be provided the email addresses of subjects' who provided their consent to allow Niraxx to access treatment adherence data. With the exception of providing email addresses to Niraxx Inc. for the purpose of monitoring treatment adherence, the investigational staff is not to provide to Niraxx Inc. information such as subject's telephone numbers, home address, personal identification numbers such as passport numbers, etc. Care must be taken by investigational staff when communicating with representatives from Niraxx Inc. in the form of telephone or electronic correspondence in not providing information (except for the email addresses of consenting subjects) that may disclose a subject's identity.

Photobiomodulation for ASD in ADHD

Documents associated with the study that are not intended to be submitted to Niraxx Inc (e.g., signed Informed Consent Forms) must be kept in strict confidence by the Investigator. Only study personnel and regulatory authority inspectors will have access to these confidential files.

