1.2. Study Discontinuation

We will encourage subjects to continue enrollment in the study via follow-up visits regardless of the nature of discontinuation of the tPBM. At the end of the study, we will refer the subjects to their counselor and/or psychiatrist and will communicate clinical data upon signed authorization. If the CGI-S increases more than 2 points during the study, the subject will be counseled to start

or change to an FDA-approved medication treatment. If the CGI-S increases more than 5 points or if a subject becomes actively suicidal as per clinician judgment, termination from the study will be mandated. Subjects who are deemed actively suicidal and are in imminent danger will be escorted to Acute Psychiatric Service (the local psychiatric Emergency Department at Massachusetts General Hospital) for evaluation and subsequent hospitalization. If the subject is appropriate for outpatient monitoring, the subject will be followed with frequent appointments outside the study. Each subject will have the Investigator's contact information as well as instructions on how to call for emergency services, if needed.

If study participation is discontinued due to safety reasons, participants will receive three follow-up visits, while appropriate psychiatric follow up access is assured with their treating psychiatrist. If emergent suicidality were to occur during the course of the study, the supervising clinician will then directly assess the level of risk and take the appropriate action (including contacting treatment providers, working on a safety plan, arranging for emergency evaluation via an ER, calling 9-1-1, etc.). The clinician will document the actions taken, and it will be noted in the participant's file. Subjects who discontinue due to non-compliance with the protocol will receive a referral to treaters in the area.

A participant may withdraw consent at any time for any reason (e.g., lack of efficacy, adverse events, etc.). A subject may be withdrawn from the study by study staff at any time if any of the following conditions are met:

- Worsening of ATs, ADHD or current/emergent major psychiatric disorder.
- Subjects who experience intolerable adverse effects as determined by the PI.
- Emergent suicidality
- Pregnancy
- Failure to keep study appointments for more than 2 consecutive visits
- Failure to utilize the telemedicine platform
- Clinical judgment of the investigator

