Subjects may receive three clinical follow-up visits at the completion of the study (or if they are required to discontinue for safety reasons), allowing adequate time for appropriate psychiatric referrals to treaters in their communities. Follow-up visits are optional and are at no cost to participants. These visits are not part of the clinical trial and no research data will be collected during follow-up. Subjects who fail to keep study appointments or are non-compliant may be dropped from the study. These study subjects will be given a referral to treaters in their area but will not be offered three follow-up visits.

If a subject would like us to forward their clinical history to his/her primary care physician, or a new clinician, we will forward any pertinent information with the proper completed release of information authorization form. If a subject who has come from the clinic of the investigator happens to drop out of the study, he or she will return to his or her treating physician.

Study Assessment Scales and Forms

Subjects will be evaluated at scheduled intervals. At each visit, measures of safety and efficacy will be obtained using assessments of psychiatric symptoms and functioning (CGIs, GAF) and measures of adverse effects (CTAE). At the Midpoint (end of week 4) and Endpoint study visits (Week 8 or Endpoint), additional clinician-, subject-, and informant-rated assessments will be repeated (see below for details).

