Considering the open-label single group design, we will rely on comparisons of the participants' performances at baseline prior to the initiation of treatment relative to their scores at the last assessment (completion/drop-visit). This design largely protects against the bias introduced by confounding factors. That is, since the same participants are tested on multiple occasions, all static confounding factors are perfectly balanced, and can have no impact on the findings. However, dynamic confounding factors may have impact on the findings (ex. Bias) and can still result from time-varying factors that are not associated with the outcomes, which is an inherent limitation of an open-label design. However, we are confident that any such factors will have a minimal impact on this study considering the duration of the trial. Since we are following subjects over a short period, missing data are not expected to impact our analyses such that standard statistical analyses will be employed. Specifically, we will employ longitudinal mixed-effects regression models (RM) with random effects for the subjects using Stata 16.0 (49). This approach has several advantages over traditional methods such as repeated measures ANOVA or MANOVA [19]. Unlike traditional methods, mixed effects RMs do not exclude subjects with missing data, can incorporate covariates (both time-varying and not) (Gibbons 1993), and can estimate the size and significance of variables predicting group outcome after accounting for individual variation in outcome. The RMs will use robust standard errors to account for the repeated measures on each subject. We will test binary data using mixed-effects logistic RMs, count data with mixed-effects Poisson RMs, and normally distributed data with mixed-effects linear RMs. Each model will predict outcome score from study visit (continuous predictor).

Primary Objective: posits that tPBM for the treatment of ATs in youth with ADHD will be safe and effective in the treatment of ATs in youth with ADHD. Our primary measure of efficacy will be the SRS-2 Total raw score which is collected at baseline, midpoint, and endpoint. The psychometric properties of the SRS have been well established as a valid measure to assess for autistic traits and can distinguish autism from other neuropsychiatric conditions (20, 50). We will examine the change in SRS-2 Total raw score over time using a mixed-effects linear RM. Our

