Withdrawal from the Study

Each subject and the Investigator reserve the right at any time to terminate a subject's participation in the clinical investigation.

Possible reasons for withdrawal or removal from the study may include:

- The subject voluntarily withdraws consent.
- The subject was not eligible based on the study inclusion and exclusion criteria.
- The subject develops an Adverse Event that would not allow continuation in the study.
- The subject has an Adverse Event which in the opinion of the Investigator warrants withdrawal from the study. Niraxx Inc must be notified within two business days.
- A decision is made by the subject and/or Investigator that the subject should be withdrawn from the study.
- Subject death
- Positive pregnancy test

When a subject withdraws or is removed from the study, the following will be performed, if feasible, at the study termination (exit) visit:

- Progress Note
- Virtual Examination of Exposure Sites
- MGH-SECS-C
- CGI
- GAF
- CTAE
- Concomitant medications form
- ADHD-SC
- SRS-2
- BRIEF-P
- TSRQ
- MGH-SECS-I
- CBCL

For all subjects who withdraw from the study prematurely, the date, and reason for withdrawal will be documented.

Lost to Follow-Up

If a clinical staff is unable to contact a subject or if the subject fails to appear for a visit, three documented phone calls should be made, followed by a certified letter (or its equivalent). The certified letter should detail the need for the subject to appear for a visit, the site's unsuccessful attempts to contact the subject, and that failure to contact the site will result in the subject being withdrawn from the study.

Photobiomodulation for ASD in ADHD

If the certified letter is returned to the site as undeliverable or the letter is delivered but the subject does not contact the site and no other contact is made with the subject or the subject's caregiver, then the subject will be considered Lost to Follow-up and discontinued from the study. All attempts to contact the subject will be documented.

VIII. POTENTIAL BENEFITS

There may be no direct benefit to subjects participating in this study. Participants may benefit by potentially experiencing improvement in ATs symptoms and by gaining knowledge about ATs.

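### Section 1.2 lets staff drop non-compliant or non-attending children from the study, not only from treatment, so the Week 8 SRS-2 data may be selected on compliance

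*Combined protocol and SAP*

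**What the plan says.** Section 1.2 (Study Discontinuation) opens with a retention aim: "We will encourage subjects to continue enrollment in the study via follow-up visits regardless of the nature of discontinuation of the tPBM". It then lists grounds on which staff may withdraw a subject. One is "Failure to keep study appointments for more than 2 consecutive visits"; another is the investigator's clinical judgment.

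Further down, the same section says "Subjects who fail to keep study appointments or are non-compliant may be dropped from the study". It gives no adherence threshold and no number of missed visits. Children dropped this way get a referral but not the three optional clinical visits. Those visits would not supply data in any case: "These visits are not part of the clinical trial and no research data will be collected during follow-up".

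Three other places bear on the point:

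- Withdrawal from the Study (under Subject Disposition Criteria): "When a subject withdraws or is removed from the study, the following will be performed, if feasible, at the study termination (exit) visit". The list that follows includes the SRS-2 and the TSRQ.
- Section VI (Biostatistical Analysis): the comparison is between baseline and the last assessment, and a drop visit counts as one. The model is a mixed-effects regression on study visit as a continuous predictor, chosen partly because it keeps subjects with incomplete data. The section expects missing data to have no impact and describes no sensitivity analysis.
- Subject Confidentiality: for subjects who consent, the manufacturer will "access treatment adherence and compliance data, which will be sent directly to the study team on a weekly basis".

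The background names acceptability as a study question ("whether it is acceptable among our patients, for whom frequent visits otherwise would be prohibitive"), and tolerability is part of the primary objective. Section VI defines no adherence or acceptability endpoint.

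**The concern.** Stopping treatment and leaving the study are different events, and section 1.2 does not keep them apart. For a device used at home, poor use and missed visits are partly results of the treatment. If those children leave the study, their later SRS-2 scores are never collected. The families who remain are then more likely to be those who use the device and find it helpful.

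The trial has no control arm, so a shift in who is measured at Week 8 goes straight into the estimated change from baseline. Because *non-compliant* is undefined and the study is open-label, removal would be decided case by case, which makes any selection hard to describe or correct later. New adverse events are also affected: section VI (Risks and Discomforts) records them only until the subject completes the study or is terminated from it.

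**Working it through.** **1. The plan's own figures.** Inputs from Sample Size: n = 60, two-sided alpha 0.05, correlation 0.5. SD of change = √(2 × (1 − 0.5)) = 1. Paired t-test power from the noncentral t distribution is 80.5% at 0.37 SD and above 99.9% at 0.8 SD; the smallest effect with 80% power is 0.368 SD. Enrolment is 60/0.67 = 89.6, so 90. All agree with the plan. The 33% attrition covers the step from 90 enrolled to 60 exposed, so it leaves nothing for exposed children without an endpoint score. If 54 or 40 of the 60 gave an endpoint score, power at 0.37 SD would be 76% or 63%.

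**2. Bias of a retained-only estimate.** Let p be the share dropped and g the amount by which their mean change is worse than in those retained (R = retained, D = dropped).

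Mean over all = (1 − p) × R + p × D, so R − mean over all = p × (R − D) = p × g.

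Neither p nor g is in the documents. Assumed ranges, in SD:

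| Dropped | g = 0.2 | g = 0.37 | g = 0.5 |
|---|---|---|---|
| 10% | 0.020 | 0.037 | 0.050 |
| 20% | 0.040 | 0.074 | 0.100 |
| 33% | 0.066 | 0.122 | 0.165 |

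The range is 0.02 to 0.17 SD. If the true average change were zero and 60 children were retained, a 5% two-sided test on them would reject in 5.3% to 24% of trials.

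**3. What exit scores do.** Assume 60 exposed, of whom 48 change by 0.45 SD and 12 by 0.10 SD.

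- All followed: (48 × 0.45 + 12 × 0.10)/60 = 22.8/60 = 0.38 SD.
- The 12 give nothing: 0.45 SD, which is 18% too high (0.45/0.38 = 1.18).
- Six of the 12 give an exit score of 0.10 SD: (21.6 + 0.6)/54 = 22.2/54 = 0.41 SD, about 8% too high.
- All 12 give an exit score with change of 0 to 0.10 SD: 21.6/60 = 0.36 to 22.8/60 = 0.38 SD.

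**4. Whether the mixed model removes the problem.** Simulation of a random-intercept model on Weeks 0, 4 and 8 with correlation 0.5. Assumed change by Week 8 is −0.5 SD if compliant and 0 if not, and every non-compliant child is dropped.

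| Dropped | All followed | Week 4 score, nothing later | Nothing after baseline | Retained only |
|---|---|---|---|---|
| 10% | −0.45 | −0.50 | −0.51 | −0.51 |
| 20% | −0.40 | −0.48 | −0.50 | −0.50 |
| 33% | −0.33 | −0.46 | −0.50 | −0.50 |

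The model keeps these children but does not recover what was not measured. A score taken at Week 4 helps only a little here, because the fitted slope is driven mainly by children measured to Week 8. A plain baseline-to-last comparison on the same assumptions, with an unchanged exit score from every dropped child, would give 0.67 × (−0.5) + 0.33 × 0 = −0.335. Section VI describes both approaches and does not say how an unscheduled exit score enters the model.

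**5. Adherence.** Assume 98% use in the 48 and 40% in the 12. Over all exposed: (48 × 98 + 12 × 40)/60 = 86.4%. Over retained children only: 98%. The gap appears only if the second denominator is used.

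**The case against.** The strongest reply is that the plan already provides for early leavers. Section VI takes the last assessment as the endpoint, a drop visit counts, and the exit visit includes an SRS-2. Nothing restricts the analysis to compliant completers. With full exit data, the example in step 3 shows almost no distortion in a last-assessment comparison. This stands, and it rules out the stronger reading that the Week 8 result *does* come from a compliance-selected sample. It does not close the gap: the exit visit depends on feasibility, families removed for missed visits are the least likely to attend it, and its score belongs to the day of removal.

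A reader might also infer that staff will use the weekly device data to remove poor users. The documents do not say so. Those data are described as internal monitoring, cover consenting subjects only, and are not tied to any removal rule. Removal is discretionary, and non-compliance with the protocol need not mean low device use.

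A reader might infer that adherence will be overstated. No adherence endpoint is defined, and use before removal is already held for consenting subjects. The 98% in step 5 is an assumed input, so its match with the adherence quoted for the pilot shows nothing.

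Nor is section 1.2 a flat contradiction. Its opening sentence is an encouragement to children who stop tPBM, and the same section lists withdrawal grounds. What remains is an undefined term, two attendance rules, and no separation between stopping treatment and ending data collection.

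Finally, the 33% upper limit borrows the plan's attrition figure, which concerns loss before exposure. It is a wide bound, not a forecast. Safety Monitoring does require adverse events to be followed to resolution, but that does not capture events that begin after removal.

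**Conclusion.** The point holds as a risk. Section 1.2 allows removal from the study for undefined non-compliance or missed appointments, and this is not reconciled with its own retention aim or its other attendance threshold. The Week 8 SRS-2 data may therefore be selected on compliance.

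The size cannot be read from the documents. On the assumed inputs (10% to 33% dropped, mean change 0.2 to 0.5 SD worse), a retained-only estimate is too favourable by 0.02 to 0.17 SD, against a detectable effect of 0.37 SD. It is less where exit scores are obtained. The simulation assumes that every non-compliant child is removed and does not change at all, so it sits at the unfavourable end. Adherence or acceptability figures are affected only if they are computed on retained children.

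This does not invalidate the primary analysis. It is a cheap improvement, worth making before data are collected, because Week 8 scores that were never requested cannot be recovered.

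**What to change.** Reconcile the statements in section 1.2 so that non-compliance or missed appointments does not by itself end data collection. State what non-compliant means, and bring the two attendance rules into agreement; which threshold to use is for the sponsor. Leave decisions about treatment unchanged.

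For a child whose treatment ends, and where consent allows:

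- keep sending the parent the SRS-2 REDCap link at Weeks 4 and 8;
- keep recording adverse events to Week 10.

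In section VI, state that all exposed subjects are analysed and how an exit SRS-2 enters the model. Compute any reported adherence over all exposed subjects with available device data.

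The cost is a wording amendment. The forms already go out by REDCap email, and collecting a questionnaire does not tie up one of the ten devices. The downside is some extra effort following up low-engagement families.

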1.2.1. Clinician-Rated Assessments

1.2.1.1. Clinician-Rated Behavioral Measures

(Administered at all visits)

- Clinical Global Impression Scale (CGI; (43)): The CGI is a measure of illness severity, improvement, and efficacy of treatment. The score for severity ranges from 1 (normal, not at all ill) to 7 (among the most extremely ill subjects). Improvement ranges from 1 (very much improved) to 7 (very much worse). The effectiveness index measures to what extent the subject is experiencing therapeutic effects in conjunction with the level of adverse events they are experiencing. CGI scales will be used for the assessment of ADHD and ATs
- Global Assessment of Functioning Scale (GAF; (44)): composite rating of an individual's overall level of functioning (1= worst to 100 = best).

(Administered at baseline and/or screening, midpoint, and endpoint)

- MGH Social-Emotional Competence Scale [Clinician-Rated Measure] (MGH-SECS-C): This is a 37-item scale that assesses change in the frequency and severity of core and associated symptoms of ASD.
- ADHD Symptom Checklist (ADHD-SC) assesses each of the individual symptoms of ADHD based on the DSM (0-3 on a scale of severity)

